# 9.2 Secondary Efficacy Analyses

The secondary outcomes are PROMs, all of which are measured on a continuous scale. Summary statistics for these outcomes at 5-years will be produced in accordance with Section 8.1.

At the time of writing, it is unclear whether it will be possible to obtain data on these outcomes at baseline, or at any other point post-surgery. If any such data is obtained, outcomes at these timepoints will be summarised in an equivalent way to the 5-year values.

If data at baseline is obtained, a comparison of the scores at baseline and 5-years will be made. If the changes in outcomes between timepoints are found to follow a Normal distribution, the paired t-test will be used to compare the change in score over time. The mean change will be reported, along with a corresponding 95% confidence interval. If the changes are not found to be normally distributed, the Wilcoxon matched-pairs test will be preferred for the analysis, whilst the median change and corresponding 95% confidence interval will be reported.

# **10 Safety Analyses**

The main safety outcome is the occurrence of adverse events and adverse device effects. The number of patients with such an adverse outcome will be reported, as will be the average number of adverse events per patient.

Additionally, a summary of all adverse outcomes will be reported descriptively as outlined in Section 8.1. The following summaries will be made:

- Description of adverse events / adverse device effects
- Related to device
- Seriousness (serious, not serious)

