#### 9.7 Subject Study Completion

Subject participation in the clinical investigation will conclude upon completion of the data collection point from 6 months to 24 months post-surgery for ACL reconstruction using the JewelACL device.

For patients who give verbal informed consent to take part in the telephone follow up, the clinical investigation will conclude upon completion of the follow up phone call.

**10.** INVESTIGATOR RESPONSIBILITIES

The role of the Investigator at each site is to implement and manage the day-to-day conduct of the

clinical investigation as well as ensure data integrity and the rights, safety and well-being of the

subjects involved in the clinical investigation. They are required to adhere to this CIP.

The Principal Investigator shall be qualified by education, training and experience to assume

responsibility for the proper conduct of the clinical investigation. Evidence of this will be provided to

the sponsor through up-to-date CVs.

Principal Investigators must be experienced and have implanted the JewelACL device for ACL

reconstruction. They must disclose any potential conflicts of interest, including financial, that

interfere with the conduct of the clinical investigation or interpretation of results, and be

knowledgeable with the method of obtaining informed consent.

Clinical Investigation Plan CRE 027 Date 14\_04\_20 Version Number 1.0

CONFIDENTIAL

Page 25 of 42

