**Unanticipated Adverse Device Effect (UADE):** 

Any serious adverse device effect on health or safety or any life-threatening problem or death caused

by, or associated with a device, if that effect, problem, or death was not previously identified in

Clinical Investigation Plan

CONFIDENTIAL

Page 27 of 42

nature, severity or degree of incidence in the investigational plan or application (including a

supplementary plan or application), or any other unanticipated serious problem associated with a

device that related to the rights, safety or welfare of the subject.

Reporting of AE

All AE's occurring during the study observed by the investigator or reported by the participant,

whether or not attributed to the device under investigation will be recorded on the CRF as specified in

the protocol. All ADE's will be recorded in the CRF.

The following information will be recorded: description, date of onset and end date, severity,

assessment of relatedness to device, other suspect drug or device and action taken. Follow-up

information should be provided as necessary.

The relationship of AEs to the device will be assessed by a medically qualified investigator or the

sponsor/manufacturer and will be followed up until resolution or the event is considered stable.

All ADE that result in a participant's withdrawal from the study or are present at the end of the study,

should be followed up until a satisfactory resolution occurs.

Where relevant, any pregnancy occurring during the clinical study and the outcome of the pregnancy,

should be recorded and followed up for congenital abnormality or birth defect.

Reporting Procedures for All SAEs/ SADEs/ UADEs

Considering the data collected in this study is on a CE marked product being used within its intended

use, and the retrospective nature of the study, all SAE/SADE/UADEs reported as part of the study

will be managed in accordance with Xiros Standard Procedure for Product Events Reports and

Vigilance.

Clinical Investigation Plan CRE 027 Date 14 04 20

Date 14\_04\_20 Version Number 1.0 CONFIDENTIAL

Page 28 of 42

**12.** STATISTICS

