# 5 Study Methods

## 5.1 General Study Design and Plan

The study is a multicentre post-market clinical follow-up, with retrospective data collection. All patients were treated with the JewelACL for ACL between 1st October 2010 to 31st December 2014, and thus all have at least 5 years follow up post-surgery. The medical records of subjects will be evaluated, and all participants will receive a telephone call to collect patient reported outcomes.

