## 7.2 Analysis Populations

The Full Analysis Population will consist of all patients recruited into the study, as long as they had a minimum of 5-years of follow-up post-procedure.

Patients with missing data at a specific outcome timepoint will be excluded from this dataset only for the particular outcome for which they had missing data.

The safety population is the same as the full analysis population

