## 7.3 Subgroups

In addition to an analysis of all patients combined, analyses for all outcomes (primary, secondary, safety) will be performed for the following subgroups:

- Patients receiving JewelACL alone
- Patients receiving JewelACL in combination with autograft

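### SAP 10 summarises adverse events per patient with no observation time or common window, so one average can mix patients observed for 24 months with patients observed for more than 5 years

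*SAP*

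**What the plan says.** SAP section 10 gives the safety statistics: "The number of patients with such an adverse outcome will be reported, as will be the average number of adverse events per patient". It adds descriptive tables of event type, device relatedness and seriousness. It mentions no person-time, rate or fixed window.

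SAP 7.3 repeats this by autograft use: "In addition to an analysis of all patients combined, analyses for all outcomes (primary, secondary, safety) will be performed for the following subgroups", namely JewelACL alone and JewelACL with autograft.

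On who is counted, SAP 7.2 says "The safety population is the same as the full analysis population". That population is everyone recruited, "as long as they had a minimum of 5-years of follow-up post-procedure". SAP 5.1 derives follow-up from the surgery dates: patients were treated between 1 October 2010 and 31 December 2014, "and thus all have at least 5 years follow up post-surgery".

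On how long events are captured, Protocol 9.7 has two rules. By default, "Subject participation in the clinical investigation will conclude upon completion of the data collection point from 6 months to 24 months post-surgery". For patients who consent to the telephone call, "the clinical investigation will conclude upon completion of the follow up phone call". Table 1 of the Protocol has record-review columns only up to 24 months, marked as depending on availability. Protocol 9.2 keeps the retrospective data of patients who do not consent to the call.

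The dates needed to measure observation time are already collected. Table 1 lists the dates of surgery and of each follow-up. Protocol section 11 (Reporting of AE) says of each event: "The following information will be recorded: description, date of onset and end date, severity".

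**The concern.** An average count per patient is interpretable only if patients are observed for similar lengths of time, or if the window is stated. Here the design makes observation unequal. A patient who is not telephoned can have events recorded for at most 24 months, while a telephoned patient can have them recorded up to a call more than 5 years after surgery. Within the telephoned group, time also varies with the date of implantation.

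The average therefore has no time horizon that a reader could attach to it. If patients who were not telephoned are in the denominator, it is also likely to understate the count over the longer period. The number of patients with an event has the same weakness.

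Reporting all recorded adverse events is a secondary objective, and Protocol 13.1 says the long-term data should give surgeons assurance about safety. A figure that non-contact can only push down is a poor basis for that.

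**Working it through.** **1. The plan's own figure, and where the 20% comes from.** SAP section 6 expects 10% re-rupture, a precision of ±6 points and 95% confidence: n = 1.96² × 0.10 × 0.90 / 0.06² = 96.04, so 96. With 20% drop-out, 96 / 0.80 = 120. Both figures reproduce. The documents give no figure for adverse events, exposure or the share of patients not telephoned. The 20% is borrowed below as an assumed share not telephoned.

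**2. Observation time.** Inputs are the surgery window above, the protocol date (14 April 2020, from the page footer) and the nine-month study period (Protocol synopsis). Assume that calls run from the protocol date to 14 January 2021.
- Shortest, telephoned: 31 December 2014 to 14 April 2020 = 5.29 years.
- Longest, telephoned: 1 October 2010 to 14 January 2021 = 10.29 years.
- Ratio among telephoned patients: 10.29 / 5.29 = 1.95. Midpoint: (5.29 + 10.29) / 2 = 7.79 years.
- Not telephoned: at most 2 years, so telephoned patients are observed 2.6 to 5.1 times as long.

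If calls start 6 or 12 months later, the range becomes 5.79 to 10.78 or 6.29 to 11.29 years.

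**3. If follow-up means elapsed time, so that everyone is counted.** Let u be the share not telephoned and s the share of a telephoned patient's events (to 7.79 years) that fall in the first 24 months. Relative to everyone being telephoned, the average is (1 − u) + u × s.

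| Event timing | s | Average at u = 0.20 | Shortfall |
|---|---|---|---|
| Constant rate (2 / 7.79) | 0.257 | 0.8 + 0.2 × 0.257 = 0.851 | 15% |
| Half by 24 months | 0.50 | 0.900 | 10% |
| 80% by 24 months | 0.80 | 0.960 | 4% |
| 95% by 24 months | 0.95 | 0.990 | 1% |

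Under a constant rate, u from 0.10 to 0.40 gives shortfalls of 7% to 30%.

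**4. If follow-up means observed time, so that only telephoned patients are counted.** The shortfall in step 3 disappears, but so do the events already recorded for the other patients. The spread in step 2 remains. A patient observed for 5.29 years has 5.29 / 10.29 = 0.51 of the expected count of one observed for 10.29 years under a constant rate, 0.84 if s = 0.80, and 0.96 if s = 0.95.

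**5. Subgroups.** With equal true event rates and equal shares not telephoned, the ratio of the two averages is 1.00. With an invented split of 10% versus 30% not telephoned, the 30% group relative to the 10% group is:
- constant rate: (0.7 × 7.79 + 0.3 × 2) / (0.9 × 7.79 + 0.1 × 2) = 6.05 / 7.21 = 0.84;
- s = 0.80: 0.94 / 0.98 = 0.96.

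**6. Would a patient-year rate be better?** Relative to everyone being telephoned, the rate at u = 0.20 is (0.8 + 0.2s) / 0.851.
- s = 0.50: 0.900 / 0.851 = 1.06, so 6% high, against 10% low for the average.
- s = 0.80: 0.960 / 0.851 = 1.13, so 13% high, against 4% low.
- The two errors are equal in size at s of about 0.60.
- For the 10% versus 30% split at s = 0.80, the false subgroup ratio is (0.94 / 6.05) / (0.98 / 7.21) = 1.14, against 0.96 for averages.

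**The case against.** The strongest reply is that SAP 7.2 already removes patients who were not telephoned. If five years of follow-up meant only elapsed time, the condition would exclude nobody, since SAP 5.1 says every patient meets it. It has an effect only if it means observed follow-up. SAP 7.2 also drops patients with missing data at an outcome timepoint for that outcome, and SAP Table 1 schedules complications at 5 years. This is a fair reading, and under it the 15%, 10%, 4% and 1% figures do not arise. It does not rescue section 10. SAP 5.1 points to the opposite reading, and the adverse event count is tied to no timepoint. Excluding these patients would also discard recorded events, against the secondary objective and against the Protocol's rule (Inclusion in Analysis) that all patients meeting the entry criteria are included. The 1.95-fold spread would remain.

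Three further objections stand:
- Several of the listed device risks (infection, laxity from misplacement or inadequate fixation) relate to the operation, so events may be mostly early and the bias small.
- The 20% is a drop-out allowance for the primary analysis, not a forecast of non-contact.
- A patient-year rate assumes a constant rate and can do worse than the average (step 6), so it should not replace it.

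A reader might also infer that the autograft comparison of adverse events is confounded. The documents do not support that. SAP 7.3 plans separate summaries, not a contrast. The objective on the effect of autograft concerns failure rates. Nothing is said about contact rate or implant year by autograft use.

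**Conclusion.** The point holds in a limited form. SAP 10 gives no observation time or common window for a study in which event capture ends at 24 months for some patients and at a call more than 5 years after surgery for others. Whether both kinds of patient enter one average depends on an ambiguity between SAP 5.1 and 7.2 that the SAP must settle. Section 10 needs an addition under either reading.

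Under the elapsed-time reading, the average can be too low by 1% to 15% at an assumed 20% not telephoned, depending on how early events occur. Under the observed-time reading, recorded events are lost and observation still varies up to 1.95-fold. These sizes rest on the assumed call dates, on the midpoint of 7.79 years and on full 24-month records for patients not telephoned.

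A reader might conclude that the average is certainly and materially biased. The documents do not show that, because they give neither the contact rate nor the timing of events. The subgroup summaries could differ for the same reason, but only if contact rate or implant year differs between them. This is a cheap improvement to a descriptive safety summary and does not threaten the primary analysis.

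**What to change.** In SAP 10, keep the planned summaries and add the following for AEs and for ADEs, overall and by autograft subgroup:
- (a) the number of patients with an event, and events per patient, within 0-24 months of surgery, for all patients with records;
- (b) the same two figures from surgery to the call, for telephoned patients only, with the median and range of observation time.

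Figure (a) puts telephoned and other patients on the same window and needs no constant-rate assumption. Figure (b) gives the long-term count a stated time horizon. Events per 100 patient-years with a 95% CI may be shown as a supplement, labelled as assuming a constant rate, but not as a replacement.

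In SAP 7.2, state that the safety population includes all enrolled patients with any post-surgery record, so that no recorded event is lost through non-contact.

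The cost is a few lines of SAP text and code and a few extra table rows, using dates already collected. The downside is that 24-month records are collected only where available and may be incomplete for some patients. The number of patients with records behind figure (a) should therefore be shown beside it.

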# **11 Technical Details**

The data analysis will be performed using the statistical software package Stata (version 15.1). Programs recording details of all data manipulation and data analyses will be produced and kept, so that the analyses can be externally inspected and, if necessary, re-run.

# 12 Summary of Changes to the Analysis Plan

The changes from version 1.0 to 1.1 of the SAP were mostly cosmetic. However, additional subgroups for the primary outcome were added (separate analyses for each fixation type), as well as the addition of demographic summaries by study site.

Between versions 1.1 and 1.2, there was a removal of the plan to analyse by fixation type, as it was felt that there was insufficient variation in the fixation types used. Additionally, a justification of the figures used in the sample size has been added.

